2) Determine if the impact of the intervention is greater for those with higher vs. lower levels of ESC, controlling for symptoms of depression and anxiety.

3) Document the feasibility and acceptability of the intervention, and explore whether the tolerability or efficacy of the intervention differs as a function of demographic variables or psychiatric symptoms.

Study Design & Methods

Sample: In order to demonstrate that the patterns of functional neural abnormalities associated with ESC can be specifically altered by cathodal tDCS, we will recruit a sample of 44 adults (18-30 years old, 50% male/female), all of whom will have clinically significant levels of depression (≥ 10 on the Quick Inventory of Depressive Symptoms^{29,30}) or anxiety (≥ 60 on the PROMIS Anxiety Short-form³¹). We are selecting a sample of depressed and anxious adults so that we can confirm that it is the ESC dimensional phenotype, and not psychiatric symptom severity, that is associated with the patterns of cortical functioning abnormalities described above. To ensure an adequate range of ESC scores, the sample will be stratified to require that half (N=22) fall in the upper tertile of ESC scores expected among adults with depression or anxiety² and half (n=22) fall in the bottom tertile.

Procedures: The proposed study will be carried out at the University of Pittsburgh, Magnetic Resonance Research Center (MRRC). Participation will occur over three assessment periods. If participants appear eligible after a telephone screen, they will be scheduled for Visit 1 (which may be virtual or in-person), during which a more thorough set of screening procedures will

determine full eligibility and demographic, symptom, trait, functioning, and life history information will be collected. If participants continue to be eligible following Visit 1, they will be scheduled for two scan visits (Visits 2 and 3) to be held on separate days, approximately one week apart. The following data will be collected:

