fMRI Protocol (Visits 2 and 3): At each scanning visit, symptoms (i.e., QIDS, PROMIS-A) will be reassessed. During fMRI at each visit, participants will complete the Cognitive Reappraisal Task. This widely used task examines the functioning of the neural circuitry associated with exerting cognitive control over the response to emotionally salient stimuli.^{34,35} Each trial begins with an instruction cue (2s) to either “attend” or “reappraise” the image that will follow. Next, a negatively or neutrally valenced interpersonally relevant picture is presented (8s) during which participants follow the instructions given for that trial. The task consists of three trial types: attend neutral, attend negative, and reappraise negative. During attend trials, participants view the scene and experience their natural emotional response. During the reappraise trials, participants are asked to reframe the meaning of the scene so as to diminish the negative emotional impact.³⁶ Participants practice the task prior to the scan, and they are provided feedback on their reappraisals of practice items. The stimulus display is followed by an emotional rating probe (4s) and finally a fixation cross (4s) to mark the end of the trial. Twenty trials of each type are presented in a pseudorandom order over two 10 minute, 20 second runs. Two versions of the task have been developed to facilitate repeated testing. These will be counterbalanced across subjects and visits. This task has been used in several studies of healthy adults,³⁷⁻³⁹ and [name] has successfully used the task in a sample of depressed individuals. Prior to fMRI scanning, structural brain data will be collected for all participants. Following the final visit, participants will complete a short, self-report questionnaire regarding their experience of the intervention and will be debriefed by study personnel.

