tDCS Protocol (Visits 2 and 3): TDCS will be administered concurrently with the emotion regulation paradigm in the scanner using procedures already in place at the MRRC. TDCS is applied to the scalp, typically providing the equivalent of what a 6V battery would produce (and providing no more than 15V). The TDCS sponge electrodes and connecting wires are non-ferromagnetic and thus can be used safely within the MRI facility. These will be connected to the main apparatus situated outside of the facility. Investigators have determined the optimal placement of wires in the scanning environment to reduce occurrence of scanning artifacts. The montage for left posterior parietal cortex stimulation and the sham will be based on our prior work, the published literature²⁶, and neurotargeting software. We will employ left posterior parietal cortex cathodal stimulation and anodal stimulation on the shoulder. Cathodal stimulation of -1mA will be used, as this produces neural inhibition⁴¹, and because higher cathodal stimulation currents can yield paradoxical excitation⁴². Voltage is controlled by the device to maintain a constant electrode -1mA current. Cathodal stimulation will be applied for the duration of the emotion regulation task (approx. 20 minutes), and it will be slowly ramped up to start and ramped down to end. Previous findings indicate that effects of acute TDCS can last about 2 hours after the procedure but not into the next day⁴². Side effects: mild skin sensations under

the electrode (itching, prickling), dizziness, visual flickering; much less frequently, nausea, headache and more serious atopic skin reactions. There is a built-in safety mechanism to prevent shorting and discomfort. Participants indicate, using a squeeze ball, if they feel scalp warmth. Sham stimulation will be slowly ramped up and down to a nominal low level (1ua).

Eligibility Criteria

Inclusion Criteria:

- 1) Between 18-30years old
- 2) Score > 10 on the QIDS or > 60 on the PROMIS-A
- 3) We will use a flexible extreme groups recruitment strategy to ensure an adequate distribution of ESC scores. We will ensure that at least 62% of the sample will be composed of those scoring .5 SD above or below the mean, as measured by the NEO-PI-R. This value corresponds to the expected values assuming a normal distribution of the trait.
- 4) Normal or corrected to normal vision
- 5) Able to provide informed consent in English
- 6) Right-handed (Annett criteria)

Exclusion Criteria:

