- 1) Have a history of head trauma with loss of consciousness.
- 2) Have a systemic medical illness that may impact fMRI measures of cerebral blood flow.
- 3) Meet standard exclusion criteria for fMRI scanning (e.g. claustrophobia, cardiac pacemakers, neural pacemakers, surgically implanted metal devices, cochlear implants, metal braces, or other MRI non-safe metal objects in the body).
- 4) Are pregnant (self-report and tested for as part of any scan by the scanning center)
- 5) Not native English speaking or not fluent
- 6) Premorbid NAART IQ estimate<85;
- 7) Visual disturbance (<20/40 Snellen visual acuity) with correction
- 8) Left/mixed handedness (Annett criteria), to ensure a uniform hemispheric dominance for interpretation of neuroimaging data
- 9) Active suicidal ideation in need of immediate treatment
- 10) Scoring below the cutoffs on both the QIDS and the PROMIS-A
- 11) History of alcohol/substance use disorder (including nicotine) and/or illicit substance use (except cannabis) over the last 3 months, determined by the MINI. Lifetime/present cannabis use (non-disordered levels) will be allowed, given its common usage in individuals in this age range.
- 13) Current or past psychotic-spectrum disorder
- 14) History of seizures

Statistical Considerations

A1: Repeated-measures ANOVA models will be used to determine whether acute cathodal tDCS to the left posterior parietal cortex, compared to the sham condition, alters patterns of neural activity in and connectivity with the posterior parietal cortex and corresponding patterns of activity and connectivity within the cognitive control network during emotion regulation. A2: Repeated measures ANCOVA models will determine whether the impact of tDCS is stronger for those with higher ESC scores, controlling for concurrent depression and anxiety symptoms. A3: Feasibility and tolerability of the intervention will be assessed by examining attrition rates between the fMRI/tDCS visits and by examining responses on the self-report questionnaire regarding the acceptability of the intervention. Differences in acceptance, tolerability, and efficacy will be explored as a function of demographic variables and psychiatric symptoms.

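### Tolerability under Aim 3 is not recorded session by session: Visit 2 is rated about a week late, and anyone who leaves after Visit 2 has no scheduled rating

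*Combined protocol and SAP*

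**What the plan says.** **Measures.** Statistical Considerations, A3, names two sources. Feasibility and "tolerability of the intervention will be assessed by examining attrition rates between the fMRI/tDCS visits and by examining responses on the self-report questionnaire". The aim behind this, in Study Objectives, is to document feasibility and acceptability and to "explore whether the tolerability or efficacy of the intervention differs as a function of demographic variables or psychiatric symptoms".

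**Timing.** The fMRI Protocol section gives one administration: "Following the final visit, participants will complete a short, self-report questionnaire regarding their experience of the intervention", with a debriefing by staff. Procedures describes "two scan visits (Visits 2 and 3) to be held on separate days, approximately one week apart".

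**What is collected at each session.** The same fMRI Protocol section says: "At each scanning visit, symptoms (i.e., QIDS, PROMIS-A) will be reassessed". These are symptom scales. No other self-report form is stated for both scan visits.

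**Expected side effects.** The tDCS Protocol section lists mild skin sensations under "the electrode (itching, prickling), dizziness, visual flickering; much less frequently, nausea, headache and more serious atopic skin reactions". There are two electrode sites: "We will employ left posterior parietal cortex cathodal stimulation and anodal stimulation on the shoulder". Participants can signal scalp warmth with a squeeze ball. No logging of those signals is described, and A3 does not use them.

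**The concern.** The expected effects are mostly short-lived bodily sensations tied to one stimulation session, whereas the only rating of them is taken once, after both sessions. Three things follow from the stated schedule, whatever the questionnaire asks:

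- The Visit 2 session is rated from about a week's memory, and the Visit 3 session with little or no stated delay.
- A participant who attends Visit 2 and does not return has no scheduled rating. If poor tolerability is the reason for leaving, that is the person whose rating matters most for Aim 3.
- The side effects that the protocol itself lists have no stated form or time point for recording them by session.

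The study is meant to supply pilot data for a later funding proposal, and A3 also explores whether tolerability varies with demographics and symptoms. Both uses are better served by a rating taken on the day, from everyone who was stimulated. The imaging analyses in A1 and A2 do not depend on it.

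**Working it through.** The plan gives no tolerability threshold, side-effect rate or dropout rate, so there is no planned figure to reproduce. The check compares the stated schedule with what A3 needs and then counts sessions.

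**Inputs**
- Planned sample: 44 (Study Design & Methods, Sample).
- Stimulation sessions per person: 2, at Visits 2 and 3 (tDCS Protocol).
- Interval between them: about one week (Procedures).
- Questionnaire: once, after the final visit (fMRI Protocol).
- Design, as read here: one active session (-1 mA) and one sham session (1 µA) per person. This is inferred from the sham comparison in Aim 1, the two tDCS visits and the repeated-measures models in A1.
- Number who attend Visit 2 and do not return, k: not given. Values of 2, 4 and 6 are assumed for illustration.

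**What each source can show**

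| Source | Visit 2 session | Visit 3 session | Leaves after Visit 2 |
|---|---|---|---|
| Attrition between visits | can follow it | cannot follow it | counted, but no side effects described |
| Final questionnaire | recalled, about 7 days | little or no stated delay | not scheduled |
| QIDS and PROMIS-A | symptoms, not side effects | symptoms, not side effects | symptoms at Visit 2 only |
| Squeeze ball | scalp warmth, no logging stated | scalp warmth, no logging stated | scalp warmth, no logging stated |

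**Session counts**
- Planned sessions: 44 × 2 = 88. At Visit 2: 44, which is 44/88 = 50%.
- With k leavers: sessions held = 88 − k; rated soon after the session = 44 − k; rated about a week later = 44 − k; no scheduled rating = k.

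| k (assumed) | Held | Soon after | About a week later | No scheduled rating |
|---|---|---|---|---|
| 0 | 88 | 44 | 44 | 0 |
| 2 | 86 | 42 | 42 | 2 |
| 4 | 84 | 40 | 40 | 4 |
| 6 | 82 | 38 | 38 | 6 |

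With the same form after each session, every session held is rated on the day and the last two columns become 0.

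**What cannot be computed.** How many of the late-rated sessions are active depends on the order of active and sham, which is not stated. The sentence "These will be counterbalanced across subjects and visits" refers to the two versions of the reappraisal task, not to stimulation. The number of active sessions rated late could be anything from 0 (all sham first) to 44 (all active first).

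**The case against.** The strongest reply is that A3 delivers what Aim 3 promises. The aim is to document acceptability and explore differences by demographics and symptoms; it plans no comparison of tolerability between active and sham. An overall rating after both sessions, read beside attrition, is a reasonable pilot measure. The questionnaire items are not given and may ask about each visit. Early leavers might be offered it. Nothing in the documents shows that itching or headache from one unusual session is forgotten within a week. Asking only at the end also avoids a mid-study prompt that might help participants guess their condition.

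Most of this stands, and it rules out three stronger readings that a reader might infer:

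- *Active side effects cannot be separated from sham.* That depends on items nobody outside the study has seen. Visit-specific items would separate them, with recall for one session.
- *Only half the active sessions inform the side-effect rate.* Computing an upper limit for an unseen side effect from 22 rather than 44 active sessions gives recalled reports no weight and assumes a 22/22 order. The documents support neither step.
- *Attrition is a faulty measure because it can follow only Visit 2.* That is true of any two-session study, and no form changes it.

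The reply does not remove the schedule itself. Visit-specific items would not shorten the week of recall, and offering early leavers the questionnaire is a possibility rather than a stated step.

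**Conclusion.** The point holds as one about timing and coverage. As scheduled, the 44 planned Visit 2 sessions are rated about a week later, each participant lost after Visit 2 leaves one session with no scheduled rating, and no form records the listed side effects by session. This rests on one questionnaire administration and on the approximate one-week gap, both stated. The number of leavers is assumed. The reading of one active and one sham session per person is inferred, and it matters only for reporting by condition.

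No gain in precision is claimed. The benefit is same-day ratings for every session held and the inclusion of early leavers. This is a cheap improvement of low priority, confined to exploratory Aim 3.

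**What to change.** After stimulation at each of Visits 2 and 3, before the participant leaves, give the same short form:

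- a checklist of the effects in the tDCS Protocol section: skin sensation or reaction at the scalp and at the shoulder, dizziness, visual flickering, nausea, headache;
- one acceptability rating.

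Add to A3: *Side effects and acceptability recorded after each session will be reported descriptively by condition. Attrition will be reported by Visit 2 condition, with reasons. Participants who do not return will be included through their Visit 2 form.*

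Keep the final questionnaire and debriefing, which can also pick up effects that begin after the participant has left. Logging squeeze-ball signals by session is an optional extra.

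**Cost.** A few minutes at each of two existing visits and three sentences in A3; no added visit. The real downside is that a checklist at Visit 2 may draw attention to sensations and prompt guesses about condition at Visit 3, which bears on the active/sham contrast in A1. An identical form at both visits limits that risk but does not remove it.
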